90 assigned (1:1 allocation) to receive either the standard of care benzathine penicillin injection or 10-
91 days of oral cefixime. The study will require 2 years to be completed and each participant will be part
92 of the study for one year.

93

94 **Methods: Participants, interventions and outcomes**

95 **Study setting {9}**

96 The study will take place in 3 primary care HIV healthcare clinics and 1 wellness center of the
97 AIDS Healthcare Foundation in Los Angeles and Oakland, California. Healthcare clinics offer HIV
98 and sexually transmitted infection (STI) primary care services while wellness centers are walk-in
99 comprehensive sexual health clinics that offer HIV/STI screening services, STI treatment and other
100 prevention services.

101

102 **Eligibility criteria {10}**

103 The inclusion criteria are:

- 104 1) Clinically or laboratory confirmed new cases of early syphilis (primary, secondary, early
105 latent syphilis) with a plasma Rapid Plasma Reagin (RPR) $\geq 1:8$
- 106 2) 18 years of age or older, capable of providing informed consent
- 107 3) HIV infected individuals must have CD4 T cell count ≥ 350 cells/mm³ and be virologically
108 suppressed (viral load < 200 copies/mL) during the past 6 months
- 109 4) Able to travel to clinic once a day or be available for phone calls or receive text message for
110 at least 7-10 days

111 The exclusion criteria are:

- 112 1) Allergy to cefixime or penicillin
- 113 2) Pregnancy or a positive pregnancy test

- 114 3) Serofast RPR titer (prior titer $\geq 1:8$ without history of 4-fold titer decline)
- 115 4) Recent (within the past 7 days) or concomitant antimicrobial therapy with activity against
- 116 syphilis, namely azithromycin, doxycycline, ceftriaxone or other beta lactam antibiotics (e.g.
- 117 amoxicillin)
- 118 5) A medical condition or other factor that might affect their ability to follow the protocol

119

120 **Who will take informed consent? {26a}**

121 Patients must provide written, informed consent before any study procedures occur (randomization,

122 blood sample collection, treatment). Consent will be obtained by a study team member in a private

123 examination room.

124

125 **Additional consent provisions for collection and use of participant data and biological**

126 **specimens {26b}**

127 Patients will also sign a Health Insurance Portability and Accountability Act (HIPAA) release form

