128 allowing access to clinical and laboratory data, including their HIV test results.

129

130 **Interventions**

131 **Explanation for the choice of comparators {6b}**

132 This is a pilot, non-comparative clinical trial designed to collect preliminary efficacy data. It

133 includes an “experimental arm” of participants receiving cefixime and a contemporaneous “control

134 arm” of participants receiving benzathine penicillin. The study was not designed to be adequately

135 powered to show a statistically significant difference in the efficacy between the penicillin and

136 cefixime arms.

137

138 **Intervention description {11a}**

139 Eligible participants who provide their consent are randomized to the two arms of the study.
140 Initially, the study team collects demographic (age, gender, race, ethnicity, contact, sexual
141 orientation) and clinical information (most recent RPR titer, CD4 T cell count, HIV viral load). A
142 venipuncture blood sample is collected by trained clinic staff and it is sent to the laboratory for
143 testing. Testing is conducted on serum using the Arlington scientific RPR test kit (Arlington,
144 Virginia) (22). Participants are randomly assigned to the two treatment groups. Participants
145 assigned to the penicillin arm will receive 1 dose of 2.4M IU benzathine penicillin G on the day of
146 enrollment. Participants who are assigned to the cefixime arm will be given 20 capsules of oral
147 cefixime 400mg on the day of enrollment to take for the following 10 days. Study staff observed
148 receipt of the first dose. Subjects in the cefixime arm will then be asked to return for a clinical
149 assessment or have a phone call assessment with the study team member 2 weeks following
150 enrolment.

151 Study staff will follow up with all participants at 3, 6, and 12 months. In each follow up,
152 participants are asked questions regarding symptoms, antibiotic use in the past 3 months and
153 number of sex partners with whom they had condom-less sex in the past 3 months. A new
154 venipuncture blood sample is also collected for RPR testing

155
156 **Criteria for discontinuing or modifying allocated interventions {11b}**

157 Participants may request to leave the study or they may be withdrawn due to study-related adverse
158 events. If a subject is discontinued from study participation due to an adverse event, they will be

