196 assume a sample size of 40 and the proportion of subjects with a 4-fold decrease in RPR from
197 baseline at 6 months to be 0.9 (90%), we would have a 95% confidence interval of (0.76, 0.97). To
198 calculate the number of subjects required to enroll to reach 40 evaluable subjects in the PP analysis
199 population, the assumptions that 20% of subjects will be excluded from the PP analysis population
200 (due to loss to follow-up or non-compliance with study medication schedule). Under that
201 assumption, enrolling 50 subjects will provide 40 subjects in the PP analysis population.

202

203 **Recruitment {15}**

204 Participant recruitment will occur in 4 AIDS Healthcare Foundation (AHF) Clinics based in Los
205 Angeles, California and Oakland, California. Study clinicians will review the medical and
206 laboratory records of syphilis cases returning for treatment before the scheduled clinical visit and if
207 the participant fulfils the eligibility criteria, they will be invited to participate in the study.

208

209 **Assignment of interventions: randomization**

210 **Sequence generation {16a}**

211 After consent, participants are randomly assigned to the study arms with a 1:1 allocation. We will
212 use a simple randomization method with a shuffled deck of sealed envelopes that contain a card
213 with the assigned treatment. The cards are created before the enrollment period and distributed to
214 each of the study sites. No other factors will be taken into consideration for randomization.

215 **Concealment mechanism {16b}**

216 The envelopes containing the randomization cards are sealed, thus the team member conducting
217 enrollment does not know the content of the envelope.

218 **Implementation {16c}**

219 The study staff will ask the participant to select a sealed envelope from the shuffled deck. After
220 selecting the envelope, the participant will reveal the treatment to themselves and the study staff.

221

222 **Assignment of interventions: Blinding**

223 **Who will be blinded {17a}**

224 This is an open label clinical trial, while neither the participants nor the study staff will be blinded
225 to the assigned treatment, staff performing statistical analyses will be masked to treatment
226 assignment.

227 **Procedure for unblinding if needed {17b}**

228 Not applicable.

229 **Data collection and management**

230 **Plans for assessment and collection of outcomes {18a}**

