231 A venipuncture blood sample will be collected at 3, 6, and 12 month visits and it will be tested for
232 RPR titer.. Study data collected on baseline include basic demographic information, sexual history,
233 laboratory tests (CD4 count, viral load, RPR titer). On each follow up visit, sexual history,
234 antibiotic use, symptoms and the RPR titer will be collected. Data will be collected on paper data
235 collection forms and will be entered into Research Electronic Data Capture (REDCap) (23, 24).

236 **Plans to promote participant retention and complete follow-up {18b}**

237 Study follow-up visits are scheduled to coincide with routine clinic appointments within AHF.
238 Study staff will send participants a 1 month, 2 week, and 1 day notification prior to their follow-up
239 appointment.

240 **Data management {19}**

241 Participant data will be collected on paper data collection forms and entered into RedCap. Data that
242 will be entered into RedCap include participant information (name, date of birth, medical record
243 number, contact information) and laboratory results.

244 **Confidentiality {27}**

245 Redcap servers are encrypted, HIPAA-compliant, password protected and accessible only by
246 designated study members. Hard copy data collection forms will be stored into a locked cabinet
247 with limited access only to designated members.

248

249 **Plans for collection, laboratory evaluation and storage of biological specimens for genetic or** 250 **molecular analysis in this trial/future use {33}**

251 There are no plans in this trial to evaluate or store biological specimen for genetic or molecular
252 analysis for future use.

253

254 **Statistical methods**

255 **Statistical methods for primary and secondary outcomes {20a}**

256 The primary analysis for the main outcome will be conducted on the “Per Protocol” (PP)
257 population. This will include participants who satisfy the inclusion and exclusion criteria,
258 completed treatment (i.e. received the penicillin injection or received all of the cefixime pills),
259 report no adverse events, returned for follow-up visits (3 and/or 6 months) and have an evaluable
260 RPR result.

261 For each treatment group, we will calculate the proportion of PP participants who achieved a 4-fold
262 RPR titer decrease at 3, or 6-months post-treatment and the exact binomial 95% confidence
263 interval.

264

265 **Interim analyses {21b}**

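### The per-protocol rule counts cefixime as completed once *received*, the sample-size section excludes non-compliance, and no record of doses taken is described

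*Combined protocol and SAP*

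**What the plan says.** Statistical methods {20a} names the primary analysis set: "The primary analysis for the main outcome will be conducted on the “Per Protocol” (PP") population. One condition for membership is that the participant "completed treatment (i.e. received the penicillin injection or received all of the cefixime pills"). The other conditions are meeting the eligibility criteria, reporting no adverse events, returning at 3 and/or 6 months, and having an evaluable RPR.

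Intervention description {11a} says how cefixime is supplied. Participants "assigned to the cefixime arm will be given 20 capsules of oral" cefixime on the day of enrolment, to cover the next 10 days. Staff observe the first dose being received. The next contact for this arm is a clinical "assessment or have a phone call assessment with the study team member 2 weeks following" enrolment; its content is not described.

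Sample size {14} assumes that 20% of participants will be left out of the PP set, "due to loss to follow-up or non-compliance with study medication schedule".

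Eligibility criteria {10}, inclusion criterion 4, requires participants to be "Able to travel to clinic once a day or be available for phone calls or receive text message for" at least 7-10 days. The text does not say what this contact is for.

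**The concern.** The same word sets different standards in the two arms. For a single injection, receiving the treatment is taking it. For a 10-day oral course handed over in one visit, receiving the capsules shows only that they were dispensed. On that reading the criterion excludes no cefixime participant, and someone who stopped after the observed first dose counts as having completed treatment.

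The sample-size section assumes the opposite. It relies on the PP set leaving out people who did not follow the dosing schedule, and the PP definition as worded cannot make that exclusion.

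The stated objective is the efficacy of a 10-day course. If the set mixes people who finished with people who did not, a disappointing proportion cannot be separated into a drug that failed and a drug that was not taken. For a pilot meant to inform later studies, that distinction matters.

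**Working it through.** **1. Reproduce the plan's figures.** Inputs from Sample size {14}: 40 evaluable, success proportion 0.9, 20% excluded.

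- Exact (Clopper-Pearson) 95% interval for 36/40: 0.763 to 0.972, which rounds to the stated 0.76 to 0.97.
- Enrolment: 40 / (1 - 0.20) = 50, as stated.

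The arithmetic is sound, so the problem lies in the definition.

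**2. Can the PP rule make the exclusion that the sample size assumes?** There are two readings.

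- *Received means dispensed.* All 20 capsules are given on day 0, so the criterion is met by every cefixime participant who is supplied. No exclusion for missed doses is possible, contrary to Sample size {14}.
- *Received means took.* The two sections then agree in intent, but the rule needs data on doses taken, and none are described:
  - {11a} and {18a} list follow-up items as symptoms, antibiotic use, sexual history or partners, and RPR.
  - {19} lists participant information and laboratory results for entry in the database.
  - {11c}, headed as adherence to interventions, covers visit scheduling, reminders and reimbursement only.
  - No capsule count, diary, adherence question or minimum number of doses appears. Figure 1 (the schedule) was not visible in the copy reviewed, so an entry there cannot be ruled out.

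**3. Illustrate the effect.** Let *k* be the number of the 10 planned exclusions (50 - 40) who are partial takers and stay in, and *r* their success proportion. The documents give neither, so both are assumptions. Completers are held at the plan's 36/40.

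PP estimate = (36 + *k* × *r*) / (40 + *k*)

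| *k* | *r* | Calculation | Estimate |
|---|---|---|---|
| 0 | any | 36/40 | 90% |
| 5 | 0.5 | (36 + 2.5)/45 | 85.6% |
| 10 | 0.5 | (36 + 5)/50 | 82% (exact 95% CI 0.686 to 0.914) |
| 10 | 0 | 36/50 | 72% |
| 10 | 0.9 | 45/50 | 90% |

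The row with *k* = 10 uses the plan's whole allowance, which is meant to cover loss to follow-up as well. The row with *r* = 0 is an extreme.

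Sample size {14} does not say whether 50 is per arm or the total. The table treats it as the number in the cefixime arm. With 25 in that arm the percentages are the same, for example (18 + 5 × 0.5)/25 = 82%, but the intervals are wider.

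**The case against.** The strongest reply is that *received* means *took*. The parenthesis explains what completed treatment means, a person who stops early has not completed it, and {11a} itself speaks of receipt when describing the observed first dose. Sample size {14} shows the same intent. This has force: a reader might infer that the plan definitely keeps non-adherent participants in the primary estimate, and the documents do not support that. They support two sections that conflict on a literal reading, and a rule that cannot be applied on the charitable one, because no adherence record is described.

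A reader might also infer that people who took nothing are counted. Since the first dose is observed, the issue is partial takers. The other PP conditions narrow it further: anyone who stopped with a reported adverse event, or did not return with an evaluable RPR, is already out.

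A larger loss is tempting too. With 30% unfinished and half of them responding, the estimate is 0.9 × 0.7 + 0.5 × 0.3 = 78%, a 12-point fall. But 30% exceeds the plan's 20% allowance for all exclusions combined, so that figure should not be used as the plan's own scale.

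Finally, retained partial takers do not inflate the cefixime result unless they respond better than completers, and the contrast between arms carries little weight in a trial declared non-comparative. Both points stand. They limit the consequence without settling who belongs in the primary set.

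**Conclusion.** The point holds as a conflict between the PP definition and the sample-size section, together with the lack of any described measure of doses taken. Following the plan as written can leave in the primary estimate partial takers who report no adverse event and return with an evaluable RPR. The likely direction is downward, assuming they respond less well than those who finish.

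On the plan's own numbers, the fall is 8 points (90% to 82%) if all 10 planned exclusions are partial takers and half respond, and about 4 points (90% to 85.6%) if 5 are. Both values lie inside the planned interval of 0.76 to 0.97. The real size depends on adherence and on response in partial takers, which the documents do not give; it is nil if everyone finishes or if partial takers respond equally well. The interval and enrolment figures themselves are correct.

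**What to change.** Reconcile {14} and {20a}. Replace the cefixime completion clause with *took all of the dispensed cefixime capsules, by capsule count or participant report*. Requiring all capsules keeps the document's own threshold. Record the item at the 2-week clinic or phone assessment already planned in {11a}.

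Three safeguards should go with it:

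- Decide PP membership without reference to RPR results. The trial is open label and recruitment was ongoing, so exclusions settled after titres are known could selectively remove non-responders and raise the estimate.
- For participants already past week 2 with no record, show adherence as unknown, and state in advance how they are classified.
- Report the same proportion and exact 95% interval for all randomised participants with an evaluable RPR, by arm, beside the PP result.

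The cost is one sentence in the definition, one data item at an existing contact, and one additional reported proportion per arm. The downside is that a few participants may leave the PP set or have unknown adherence. If no more than the planned 20% are excluded in total, the 50-to-40 calculation is unaffected.

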159 evaluated by the study clinicians for the need of additional treatment for syphilis. Safety data will
160 be collected on any subject who is withdrawn from the study.

161 Participants in both study groups may receive additional treatment with penicillin, if they show no
162 response to treatment (stable or absence of 4-fold decline at 6 months).

163

164 **Strategies to improve adherence to interventions {11c}**

165 To ensure retention of participants, follow-up visits will be scheduled to coincide with routine clinic
166 appointments for HIV care or preventive sexual health appointments, which occur every three
167 months. In addition, study staff will contact participants, either over the phone or via text message,
168 before their scheduled follow-up appointment. Finally, participants will receive reimbursement for
169 their time and transportation in the form of a gift card.

170

171 **Relevant concomitant care permitted or prohibited during the trial {11d}**

172 Usual HIV care and treatment for the participant will continue throughout the trial. Concomitant
173 antibiotic use during the participation in the study duration of the trial will be recorded.

174

175 **Provisions for post-trial care {30}**

176 Once participants complete the study, they will be able to continue receiving clinical care from the
177 clinics. Participants study records will be reviewed and if necessary, additional treatment for
178 syphilis will be administered according to the standard of care protocol.

179

180 **Outcomes {12}**

181 The primary outcome is the successful treatment of early syphilis by the 3-, or 6-month follow-up.
182 The participants' RPR titer will be used as the primary measure of outcome. Successful treatment is
183 defined as an equal or greater than 4-fold RPR titer decrease, from baseline to 3 or 6 months after
184 treatment.

[figure not shown]
185

186 **Participant timeline {13}**

187 Participants will be part of the study for 12 months. Study evaluations will occur at 3, 6- and 12-
188 months post-treatment. See Figure 1 for the participant timeline for the trial.

189

190 **Figure 1: Participant Enrollment and Follow-Up Schedule**

191

192

193 **Sample size {14}**

194 The primary analysis will compute the proportion of subjects with a 4-fold decrease (from study
195 entry RPR) in RPR titer from baseline at 6 months in the per protocol analysis population. If we

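### The per-protocol set, the only efficacy population in the plan, drops anyone who reports an adverse event, so each arm's success proportion is conditioned on something treatment can cause.

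*Combined protocol and SAP*

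**What the plan says.** Section {20a} (Statistical methods for primary and secondary outcomes) places the primary analysis on the per-protocol set. Members must meet the eligibility criteria, have completed treatment, and "report no adverse events, returned for follow-up visits (3 and/or 6 months) and have an evaluable" RPR result. The success proportion and its exact 95% interval are then computed in this set for each arm. Section {14} (Sample size) uses the same set: the proportion with a 4-fold fall is taken from "entry RPR) in RPR titer from baseline at 6 months in the per protocol analysis population". No intention-to-treat, all-treated or sensitivity population appears anywhere.

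Four other places bear on how the clause is read:

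- **Section {14}** allows for 20% exclusion from the per-protocol set and names the reasons: "due to loss to follow-up or non-compliance with study medication schedule). Under that". Adverse events are not among them.
- **Section {11b}** links adverse events to leaving the study: "Participants may request to leave the study or they may be withdrawn due to study-related adverse" events.
- **Section {20a}** explains completed treatment, for cefixime, as having received all the pills. Section {11a} describes a single hand-out on the day of enrolment: "Participants who are assigned to the cefixime arm will be given 20 capsules of oral" cefixime.
- **Section {11a}** gives the cefixime arm alone a further contact, a clinic "assessment or have a phone call assessment with the study team member 2 weeks following" enrolment.

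**The concern.** An adverse event happens after randomisation and can be caused by treatment; section {11b} itself foresees study-related events. Selecting on its absence changes the question. The objective in section {7} is the efficacy of cefixime, and the outcome in section {12} is a fall in RPR titre, with no mention of tolerability. The clause turns the estimate into efficacy among people who reported no adverse event.

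The bias is nil on average if adverse events are unrelated to response, upward if reporters fail more often than others, and downward if they fail less often.

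Two features of the design could make the exclusion uneven. Only cefixime participants have the 2-week contact, and participants and site staff know the assignment, so the opportunity to report may differ by arm. Symptoms are also asked about at every follow-up. With no limit by cause or timing, nothing in the wording stops a symptom of persisting infection from being counted as an adverse event, which would remove a treatment failure. The documents do not say that either happens; they leave both open.

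No between-arm test is planned. What is at stake is each arm's own proportion, which is the only efficacy result the plan specifies.

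**Working it through.** **Inputs from section {14}:** 40 per-protocol participants, 90% success, stated interval (0.76, 0.97), 20% exclusion, 50 enrolled. **Assumed, because the documents give no figure:** the number of adverse-event reporters and how many of them fail. Treating the 40 as one arm is also an assumption; the section does not say whether it is per arm or in total.

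**1. The plan's own figures.** The Clopper-Pearson 95% interval for 36/40 is (0.763, 0.972), which matches. Enrolment is 40/(1 − 0.20) = 50, which also matches.

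**2. Effect on the estimate.** Start from 36 successes among 40 treated and evaluable participants. Let k be the number of reporters and f the number of the 4 failures who are reporters. Then

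per-protocol proportion = (36 − k + f)/(40 − k).

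With k = 8 (20%), the last column gives the hypergeometric probability of each split if adverse events and failure are unrelated:

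| f | Per-protocol result | Exact 95% CI | Probability, no association |
|---|---|---|---|
| 0 | 28/32 = 87.5% | 0.710–0.965 | 0.393 |
| 1 | 29/32 = 90.6% | 0.750–0.980 | 0.434 |
| 2 | 30/32 = 93.8% | 0.792–0.992 | 0.152 |
| 3 | 31/32 = 96.9% | 0.838–0.999 | 0.020 |
| 4 | 32/32 = 100% | 0.891–1 | 0.0008 |

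With no association the expected f is 8 × 4/40 = 0.8, so the expected proportion is 28.8/32 = 90.0%: no bias on average. At f = 2, 2/8 = 25% of reporters fail against 2/32 = 6% of the others, and the estimate rises by 3.8 points.

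Other assumed rates: k = 4 with f = 1 gives 33/36 (91.7%); k = 12 with f = 2 gives 26/28 (92.9%).

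**3. The other starting point.** Section {14} gives 40 and 90% as per-protocol figures. If 36/40 is already the result after exclusion, adding back 8 reporters gives 43/48 (89.6%) if one failed and 42/48 (87.5%, CI 0.75–0.95) if two failed. The bounds are 36/48 (75.0%) and 44/48 (91.7%).

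**4. Effect on the planned number.** With 50 enrolled and 10 excluded for the two reasons named in section {14}, the planned 40 becomes:

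| Adverse-event rate (reporters of 50) | Full overlap with the 10: 40 − max(0, reporters − 10) | Independent: 40 × (1 − rate) | No overlap: 40 − reporters |
|---|---|---|---|
| 10% (5) | 40 | 36 | 35 |
| 20% (10) | 40 | 32 | 30 |
| 30% (15) | 35 | 28 | 25 |

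**5. If 40 is the total, about 20 per arm.** With 4 reporters, 18/20 becomes 14/16 (87.5%), 15/16 (93.8%) or 16/16 (100%) as 0, 1 or 2 reporters fail.

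**The case against.** The strongest reply is that the clause was meant more narrowly. Elsewhere adverse events touch the efficacy data only through withdrawal, and the exclusion reasons in section {14} do not mention them. The authors may have had in mind people withdrawn for study-related events. The clause would not then be wholly redundant, because receiving all the pills could mean being handed them at enrolment. That reading is possible, but the text does not state it, and an analyst who follows section {20a} would drop every reporter. The silence of section {14} shows a mismatch between the two sections; it does not narrow the clause.

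A second reply concerns size. Every rate and split above is assumed, and the most likely split with no association moves 90.0% to only 90.6%. A shift of 3.8 points lies well inside the planned interval, and two or more reporter failures has probability 0.152 + 0.020 + 0.0008 = 0.17 with no association at all. This stands: no particular bias is shown. It does not rescue the rule, which changes what is estimated whatever the size, and no other planned analysis would reveal the effect.

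A third reply is the trial's modest aim: "This is a pilot, non-comparative clinical trial designed to collect preliminary efficacy data. It" has no between-arm test. True, but each arm's proportion is then the whole efficacy result.

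Finally, replacing a primary population during an open-label trial has its own risk, and defining the clause while adding a second population would be milder. That would expose the effect, but the headline figure would still carry the selection.

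**Conclusion.** The concern holds, and the population should be changed before the outcome data are analysed by arm. That treated, evaluable participants are excluded on a post-randomisation variable follows from section {20a} as written. The size of the effect does not follow from the documents. With 20% reporters assumed and 40 taken as one arm, plausible shifts run from under 1 point to about 4 points. The outer bounds are 87.5% and 100%; the upper one needs all four failures to be reporters. The planned 40 falls to 32 at that rate if adverse events are independent of the other exclusions, and to between 30 and 40 depending on overlap.

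**What to change.** - Delete the adverse-event condition from the per-protocol definition in section {20a}, and report adverse events by arm as safety data.
- In the same amendment, say whether completed treatment means capsules taken or handed out, so that it agrees with the non-compliance exclusion in section {14}. The deletion depends on this: if it means handed out, a cefixime participant who stopped early would stay in the set.
- Add, for each arm, the success proportion with exact 95% interval among all randomised participants with an evaluable 3- or 6-month RPR. Note that this set still conditions on return and evaluability.
- Date the change before outcome data by arm are analysed, and record who has seen the success proportions sent to the DSMB under section {21b}.

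**Cost.** The change alters the primary population while recruitment continues, so it needs a documented amendment to the IRB and the DSMB. Section {17a} says that, although sites know the assignment, "to the assigned treatment, staff performing statistical analyses will be masked to treatment" assignment; this reduces the concern about a mid-trial change but does not remove it. The deletion and the extra row need no new data, because RPR is already collected at both visits. If capsules taken is chosen, the source must be named, since the documents do not say what the 2-week contact records.

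### As {20a} is written, a participant with only a month-3 RPR and no 4-fold fall counts as not successful although the month-6 result is unknown, which can only lower the estimated response by month 6

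*Combined protocol and SAP*

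**What the plan says.** Outcomes {12} sets a window that runs to month 6: "The primary outcome is the successful treatment of early syphilis by the 3-, or 6-month follow-up". Success is "defined as an equal or greater than 4-fold RPR titer decrease, from baseline to 3 or 6 months after" treatment, so a fall at either visit is enough.

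Statistical methods {20a} makes the per-protocol set primary. Besides eligibility and completed treatment, members must "report no adverse events, returned for follow-up visits (3 and/or 6 months) and have an evaluable" RPR result. The and/or makes one visit sufficient, including month 3 alone. The estimate is then defined: "For each treatment group, we will calculate the proportion of PP participants who achieved a 4-fold" "RPR titer decrease at 3, or 6-months post-treatment and the exact binomial 95% confidence" interval. The denominator is every per-protocol participant in the group.

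Two other places fix the time point at month 6. Sample size {14} describes the same primary analysis as the proportion with a 4-fold decrease, "entry RPR) in RPR titer from baseline at 6 months in the per protocol analysis population. If we", and attaches its 90% assumption to month 6. The provision on additional treatment in {11b} describes non-response by the titre at 6 months.

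Nowhere do the documents say how a missing month-6 RPR is handled. There is no imputation rule, no sensitivity analysis, and no definition of an evaluable result.

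**The concern.** Take two hypothetical participants with baseline 1:32 and month-3 titre 1:16. One returns at month 6 with 1:8 and is a success. The other does not return. That person meets the follow-up requirement through the month-3 visit, has no 4-fold fall on record, and sits in the denominator only. The first was given 6 months to respond, the second 3, and only attendance separates them.

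The error is one-sided. A participant seen only at month 3 who has responded is correctly a success, because a fall at either visit satisfies {12}. A participant seen only at month 3 who has not responded has an undetermined outcome but is scored as if it were known. The reported proportion therefore mixes response by 3 months with response by 6 months and falls below the latter.

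The proportion and its interval are the main result of this pilot, and the Discussion offers the data as a foundation for later work. A reader would take the figure as response by month 6.

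**Working it through.** **1. The plan's own figures.** From {14}: 40 evaluable, response 0.90 at 6 months, 95% interval (0.76, 0.97), 20% excluded from the per-protocol set, 50 enrolled. The exact (Clopper-Pearson) interval for 36/40 is (0.763, 0.972), which rounds to the stated limits, and 40/(1 − 0.20) = 50. Both reproduce, for an endpoint known at month 6 in everyone.

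**2. How {20a} classifies each pattern.**

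| RPR available | 4-fold fall seen | Counted as | True status by month 6 |
|---|---|---|---|
| Months 3 and 6 | at either visit | success | success |
| Months 3 and 6 | at neither | not successful | not successful |
| Month 6 only | yes / no | success / not successful | as counted |
| Month 3 only | yes | success | success |
| Month 3 only | no | not successful | unknown |

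Only the last row is at fault. (For month-6-only participants without a fall, the table takes it that there was none at month 3 either.)

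**3. Expected size.** Let u be the share of the set seen only at month 3 and p3 the response by month 3. Neither is in the documents, so both are assumptions. Take 0.90 as response by month 6 (from {14}) and assume attendance is unrelated to response. The expected proportion is

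(1 − u) × 0.90 + u × p3 = 0.90 − u × (0.90 − p3).

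| p3 | u = 5% | u = 10% | u = 20% | u = 30% |
|---|---|---|---|---|
| 0.60 | 0.885 | 0.870 | 0.840 | 0.810 |
| 0.70 | 0.890 | 0.880 | 0.860 | 0.840 |
| 0.80 | 0.895 | 0.890 | 0.880 | 0.870 |

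**4. In people.** The expected number misclassified among 40 is 40 × u × (0.90 − p3). At u = 10%, 20% and 30% this is 1.2, 2.4 and 3.6 for p3 = 0.60, and 0.8, 1.6 and 2.4 for p3 = 0.70. Each one costs 1/40 = 2.5 points:

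- none: 36/40 = 0.900 (0.763, 0.972)
- one: 35/40 = 0.875 (0.732, 0.958)
- two: 34/40 = 0.850 (0.702, 0.943)
- four: 32/40 = 0.800 (0.644, 0.909)

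{14} does not say whether 40 is a total or a number per arm. If it is a total split evenly (an assumption), each arm has 20 and each misclassified responder costs 5 points: 18/20 = 0.90 (0.683, 0.988) becomes 17/20 = 0.85 (0.621, 0.968).

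**5. Dropping the undetermined overshoots.** If month-3-only non-responders are removed but month-3-only responders kept, the expected value is [(1 − u) × 0.90 + u × p3] / [(1 − u) + u × p3]. For p3 = 0.70 this is 0.907, 0.915 and 0.923 at u = 10%, 20% and 30%.

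**6. The two bounds contain the target.** The undetermined share is u × (1 − p3). At u = 20% and p3 = 0.70 it is 0.06, so the bounds are 0.86 and 0.86 + 0.06 = 0.92, either side of 0.90.

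**7. Kaplan-Meier on the two visits.** Month-6-only participants would be treated as observed non-responders at month 3. With p3 = 0.70, 20% month-3-only and 20% month-6-only, 0.80 × 0.70 = 0.56 respond at month 3, leaving 0.44. Censoring removes 0.20 × 0.30 = 0.06, leaving 0.38 at risk, of whom 0.80 × 0.10 = 0.08 have not responded at month 6. The estimate is 1 − 0.44 × 0.08/0.38 = 0.907, not 0.90.

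**The case against.** The plan never says that a month-3-only non-responder is a failure. That classification is inferred from the numerator and denominator. What makes an RPR result evaluable is undefined, and {14} places the analysis at 6 months and lists loss to follow-up as a reason for exclusion, so a team reading {14} might leave this person out. This stands as a caution on wording. It does not remove the problem: {20a} is the section that defines the set, its and/or admits the participant, and two sections that lead to different denominators need reconciling.

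The bias is conservative. Scoring unknown as non-response is a common convention, and here it cannot make cefixime look better than it is. That is right and limits the harm, but the convention should be stated, with its effect shown.

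The size is assumed. Visits are scheduled with routine appointments, with reminders and reimbursement, so the month-3-only share may be small, and any such share comes on top of the 20% already excluded. The shifts in the table all lie inside the planned interval of 0.76 to 0.97. These points stand, although that interval describes sampling error and does not allow for a systematic shift.

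A reader might infer that the rule distorts a comparison of the arms, because attendance could differ in an open-label trial. The documents do not support this as a harm. The trial is described as non-comparative, {20a} plans only a proportion and interval per group with no between-arm test, and nothing suggests that month-6 attendance differs by arm.

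**Conclusion.** The point holds as an inconsistency in the primary analysis with a one-directional effect. On the plain reading of {20a}, an unknown month-6 result after a month-3 non-response is counted as not successful, while {14} and {11b} look to month 6. Response by month 6 can only be understated as a result.

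With 90% response by month 6, 60–80% by month 3, and a month-3-only share of 10–20%, the expected figure is 84–89%. This rests on the assumed month-3 rate and share and on attendance being unrelated to response. If nearly everyone attends month 6, the effect is negligible. At 40 evaluable it amounts to a few people at most over the range examined.

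A reader might also infer that the sample size or its interval is wrong. They are not: both reproduce for a month-6 endpoint. Nor do the documents make a case for replacing the exact binomial estimate by Kaplan-Meier as the main result. It would rest on uninformative censoring, which cannot be tested here, and it mishandles participants seen only at month 6.

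**What to change.** In {20a}, class a participant with only a month-3 RPR and no 4-fold fall as undetermined. Word {12}, {14} and {20a} alike, as response by month 6. The time point in {11b} is a matter of clinical management and is cited here only to show the inconsistency.

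For each arm, report the number undetermined and give the proportion with its exact 95% interval twice: all undetermined as failures, then all as successes. For example, 34 successes, 2 undetermined and 4 failures would be shown as 34/40 = 0.850 (0.702, 0.943) and 36/40 = 0.900 (0.763, 0.972). Do not drop the undetermined while keeping month-3-only responders, since that biases the estimate upward (step 5).

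As an optional sensitivity analysis, estimate cumulative response by month 6 with a method that allows for censoring at month 3 and for interval censoring in month-6-only participants, and state that it assumes attendance is unrelated to response.

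The cost is a few lines of text and a little more analysis, on data already collected. The drawback is that the main result appears as a range whenever anyone is undetermined.
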